2.1. Background

Reactive oxygen species (ROS) are natural products of oxygen metabolism in living cells (1–3). Excessive ROS production triggers oxidative stress in the human body (4, 5). The long-term exposure to oxidative stress has been demonstrated to be a contributing factor to the development of several degenerative diseases, including cardiovascular disease, cancer and various other chronic conditions. These diseases currently represent the leading causes of mortality in the human population (6–8). In 2019, the global mortality rate was 28% higher than in 2000. The number of cardiovascular disease cases in Indonesia reached 2,784,064, while diabetes mellitus cases reached 16 million (9). The World Health Organization (WHO) also reports cancer as the leading cause of death worldwide, with 10 million deaths in 2020 (10, 11).

The prevalence of degenerative diseases in contemporary society is attributable to a multitude of factors, chief among which is an unhealthy lifestyle that engenders excessive ROS formation. Antioxidants are vital for neutralizing and reducing ROS production in the body. White tea (*Camellia sinensis*) is one such antioxidant whose potential for exploration is significant (12). Catechins and polysaccharides have been identified as the bioactive compounds responsible for the wide range of biological activities exhibited by white tea, which include hypoglycemic, hypolipidemic, and antioxidant properties (13). Previous studies have reported that EGCG and EGC are capable of regulating gene expression in cholesterol metabolism, such as low-density lipoprotein receptor (LDLR), microsomal triglyceride transfer protein (MTTP), and apolipoprotein B (APOB) (14). Supported by other studies, white tea has been shown to suppress the adipogenesis process by increasing lipolytic activity (15). It has been documented that white tea has the capacity to reduce creatinine and blood urea nitrogen levels in female rats afflicted with kidney disorders induced by cisplatin (16). As demonstrated in our preceding preclinical research, a dose-response relationship has been observed between white tea consumption and several parameters, including ALT, AST, lipid profile, red blood cells, haematology, and haematocrit, in healthy rats. It was hypothesised that the most significant increase in ALT and AST values would occur at higher doses. This hypothesis was tested, and it was concluded that 0.072 mg/day of white tea (equivalent to a human dose of 4 g/day) was more effective than 0.144 mg/day (equivalent to a human dose of 8 g/day). This phenomenon may be attributable to the production of pro-oxidants, a consequence of the elevated antioxidant content present in high concentrations of white tea. The objective of this study was twofold: firstly, to analyze the effectiveness of a 4 g/day dose in humans on human health parameters; and secondly, to ensure the safety of using this dose for 14 days.

2.2. Product Dosage

The dosage employed in the clinical trials pertains to in vivo studies conducted on both normal Wistar rats and CCl₄-induced rats, with varying doses of white tea ranging from 0.072 to 0.144 milligrams per kilogram of body weight, administered over a period of 14 days. In consideration of the findings and the outcomes of an analysis of numerous parameters, including complete haematology (RBC, Hb, Hct, MCV and MCH), biochemistry (ALT, AST, total cholesterol, LDL, HDL and triglycerides), and antioxidant enzyme activity (SOD, CAT, and GPx), it was determined that a dose of 0.072 mg/kg BW exhibited the most efficacious and secure effect on these parameters. The 0.072 mg/kg BW dose for rats was adopted from the conversion of a 4 gram/day

human dose. The present study will utilize a dosage of 4 grams of white tea in 200 millilitres of water, to be consumed on a daily basis for a period of 14 days.

2.3. Known Risks and Potential Health Benefits of White Tea Consumption

Possible risks associated with drinking white tea that have been studied:

- White tea contains theophylline and caffeine (17). Theophylline has been demonstrated to induce acid reflux, a factor which can precipitate the development of erosive oesophagitis. Consequently, the burning sensation experienced by the subject may be attributable to elevated levels of theophylline entering the body. The presence of caffeine in white tea has been demonstrated to induce adverse effects, including symptoms such as nausea and vomiting.
- Caffeine, a stimulant compound found in tea, has been observed to induce calcium release, thereby facilitating increased muscle contractions. Furthermore, it has been demonstrated that caffeine can induce the secretion of stimulatory agents such as prostaglandin, adenosine triphosphate, acetylcholine and nitric oxide from the urothelium, thereby stimulating augmented urine production in the bladder (18).
- Catechins, a type of polyphenol found in white tea, have been shown to possess therapeutic benefits in treating various diseases. However, in excessive doses, they have the potential to cause excessive pro-oxidant effects, triggering inflammatory reactions, necrosis and steatosis in the liver (18).
- The high polyphenol content of white tea has been demonstrated to have a potential inhibitory effect on iron absorption, which may consequently result in iron deficiency and the subsequent development of anaemia (19–21).

Benefits associated with drinking white tea that have been studied:

- Catechins and polysaccharides are believed to be responsible for the broad biological activity exhibited by white tea, which includes hypoglycaemic, hypolipidaemic, and antioxidant properties (13).
- The ingestion of green tea (*Camellia sinensis*) for a period of two months has been demonstrated to engender favourable outcomes in elderly subjects afflicted with metabolic syndrome. These outcomes encompass a reduction in weight, BMI, and waist circumference (22).
- The administration of three cups of green tea infusion (7.5 g/day) has been demonstrated to enhance the lipid profile in patients with T2DM nephropathy, without compromising renal function (23).
- It has been demonstrated that EGCG, a polyphenol compound found in green tea, possesses the ability to regulate glucose homeostasis by promoting glucose uptake in adipocytes, reducing insulin resistance, and decreasing blood glucose levels (24).
- Green tea (600 mL/day) for 4 weeks was reported to maintain the health of healthy respondents. This was evidenced by no significant changes in haematological profile (RBC, Hb, Hct, MCV, and MCH), serum creatinine, eGFR, and serum urea (25).
- The ingestion of three cups of green tea (100 mL per cup) per day has been demonstrated to enhance the activity of superoxide dismutase (SOD), catalase (CAT), glutathione (GSH), and glutathione peroxidase (GPx) in chronic smokers(26).

3. REASONS AND OBJECTIVES OF THE RESEARCH

3.1. Justification for Study

A plethora of studies conducted in various countries, including China, Japan, and Turkey, have demonstrated the health benefits of white tea, including its potential as an anticancer, anti-obesity, antihyperlipidemic, and antidiabetic agent. Geographical differences in the countries where *Camellia sinensis* tea is cultivated will affect its chemical composition. A review of the extant literature reveals a paucity of studies exploring the potential of white tea from Indonesia for human health. The present study will examine the antioxidant capacity of white tea, with a view to providing new references for the public regarding white tea products as antioxidants that can be used as products to improve public health.

3.2. Research objectives

The objectives of this study are:

1. Determine the effect of white tea consumption on the anthropometry of healthy subjects based on body weight, body mass index (BMI), waist circumference, and blood pressure.
2. Determine the effect of white tea consumption on biochemical parameters in healthy subjects based on blood sugar levels, complete lipid profile (total cholesterol, low-density lipoprotein, high-density lipoprotein, and triglycerides), liver function activity (based on liver enzyme function including alanine aminotransferase and aspartate aminotransferase), and kidney function (through measurement of creatinine levels, estimated glomerular filtration rate, and urea nitrogen levels).
3. Determine the effect of white tea consumption on hematology profile parameters associated with anaemia, including total red blood cell count, haemoglobin, haematocrit, mean corpuscular haemoglobin (MCH), and mean corpuscular volume (MCV).
4. Determine the effect of white tea consumption on the first line antioxidant enzymes activity of healthy subjects, such as superoxide dismutase, catalase, and glutathione peroxidase.

4. STUDY DESIGN

The present study adopts a quasi-experimental design, conducted as a pilot study, with the objective of ascertaining the effect of white tea consumption on several human health parameters. These parameters include anthropometry, blood pressure, haematology, biochemistry, and antioxidant enzyme activity. The study is divided into three stages. Firstly, a washout stage is conducted over the first seven days. This is followed by an intervention/treatment stage for 14 days, which is conducted one day after blood sampling. Finally, an observation stage is conducted for the last seven days to ensure that the subjects are in good condition after the intervention.

6. TARGET POPULATION AND SAMPLE SIZE

The population utilised in this study comprised healthy subjects residing at Padjadjaran University and its environs who had completed the recruitment form on Google Forms. The respondents' data that had been entered underwent preliminary screening based on the following inclusion and exclusion criteria.

Inclusion criteria

- a. Participants are members of the Padjadjaran University community and surrounding areas aged 20-35 years (excluding women who were either unmarried or sexually inactive).
- b. Participants must not have been smokers for less than 5 years.
- c. Participants must not have a history of anaemia, liver or kidney disease.

Exclusion criteria

- a. Participants were required to take certain medications or vitamin supplements.
- b. The subjects reported experiencing discomfort during the administration of the product.
- c. Prior to the initiation of treatment, biochemical results were found to be outside the normal range.

This study utilised a pilot study, and the minimum sample size calculation was performed using the thumb method with a non-central t-distribution (NCT) approach. Whitehead stated that the minimum sample size for a power (β) value of 90% and a significance (α) value of 5% is 15 for each group. Considering a 20% possibility of dropouts, we used 19 subjects in the study. The following table provides a reference for the calculation of the sample size, as outlined by Whitehead et al. (2016) (27).

Table 8. Estimated stepped rules of thumb for required pilot trial sample size per treatment arm when the NCT approach will be used to calculate the main trial sample size.

Standardised difference	80% powered main trial	90% powered main trial
Extra small ($\delta < 0.1$)	50	75
Small ($0.1 \leq \delta < 0.3$)	20	25
Medium ($0.3 \leq \delta < 0.7$)	10	15
Large ($\delta \geq 0.7$)	10	10

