The total number of subjects included in the study was 19, with an age range of 20-35 years (excluding women who were either unmarried or sexually inactive). These subjects resided in the vicinity of Padjadjaran University and had provided written consent by signing an informed consent form. The subjects must be in good health, have not been active smokers for a period of less than five years, and have no history of anaemia, cardiovascular disease, or liver and kidney disorders. The exclusion criteria employed are outlined below:

- a. Participants were required to take certain medications or vitamin supplements.
- b. The subjects reported experiencing discomfort during the administration of the product.
- c. Prior to the initiation of treatment, biochemical results were found to be outside the normal range.

Consent to Respondents

Informed consent will be requested by the research team before the washout period begins. Consent will be given in writing in the form of a signed consent form by the respondents.

Respondents Recruitment

The patient recruitment process was executed through the dissemination of advertisements utilising Google Forms, which were subsequently propagated via social media WhatsApp groups and Instagram. Following an initial screening process based on the information provided in the Google Forms by prospective research subjects, the research team made a selection based on inclusion criteria to obtain patients who met the specified criteria.

Test Product

The test product provided was 4 grams of white tea, packaged in a tea bag. The respondents were instructed to brew one tea bag in 200 mL of hot water for 10 minutes. The ingestion of the white tea should be scheduled for one hour prior to or two hours after breakfast.

Monitoring During Intervention

During the white tea intervention process, subjects will be monitored for food and beverage intake and daily activities. Please refer to Appendix 1 for a comprehensive overview of the daily data.

Research Duration

The research is estimated to take 28 days, including the first seven days for the washout phase, the second 14 days for the intervention phase, and the last seven days for the observational stage. This is to ensure that the subjects do not experience any serious effects as a result of the research.

Data Collection

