7.4. Provision of Test Products

Following the endorsement of the consent form, each subject will be furnished with a set of fourteen tea bags, each containing four grams of white tea. These tea bags will be accompanied by comprehensive instructions detailing the optimal preparation of the tea. Subjects are instructed to brew one tea bag in hot water for 10 minutes. The tea must be consumed one to two hours after breakfast for a period of 14 days.

Product Storage

White tea products should be stored in a sealed container at room temperature.

Guarantee of research subject compliance

Subject compliance will be monitored each morning by asking subjects to send a video of themselves drinking the beverage product every day.

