7.5. Respondent Monitoring

Monitoring of anthropometry and blood pressure

The subjects of the research will undergo physical monitoring, including weight, height, BMI, waist circumference and blood pressure, by research team on days 0 and 15 (one day before and one day after the last day of the white tea intervention).

Laboratory monitoring

Laboratory monitoring was conducted on days 0 and 15 (one day before and one day after the last day of the white tea intervention) on blood samples from subjects in order to determine the effects of drinking tea for a period of 14 days. Should the preliminary investigative results pertaining to haematological parameters (RBC, HB, HCT, MCV and MCH), ALT, AST, serum creatinine levels, eLFG and urea nitrogen levels demonstrate abnormality, the subject will be withdrawn from the study for reasons of safety. Haematological tests are performed to ensure that the subject is not anaemic. ALT and AST tests are performed to ensure that there is no liver dysfunction, while serum creatinine, eGFR, and urea nitrogen tests are performed to ensure that the subjects do not have kidney dysfunction. In summary, the parameters employed in this study to observe the effects of white tea consumption are outlined as follows:

- a. Hematology profile
- b. Lipid profil
- c. Fasting blood glucose
- d. ALT dan AST
- e. Serum creatinine level, urea nitrogen level and eGFR
- f. First line antioxidant enzymes (SOD, CAT dan GPx).

Monitoring consumption and daily activities

In order to ensure that respondents adhere to the prescribed dietary regime, researchers will ensure that subjects abstain from the consumption of particular products that must be avoided during the course of the research process. Researchers will record all food and beverages consumed, the subjects' daily activities, and any complaints that may be experienced by the subjects, whether related or unrelated to the administration of white tea products.

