APPENDIX 1. SCREENING FORM FOR SUBJECTS

SAMPLE

Research Number:	Respondent's initials: [] [] []
------------------	------------------------------------

SCREENING 1 – PERSONAL DATA

PERSONAL DATA		Officer ()
Date of data collection	: [] / [] / [] (DD/MM/YY)	
Name / initial	: [] [] []	
Place and Date of Birth		
Age	: Tahun	
Gender	: Pria / Wanita *	
Job	:	
Address	:	
Contact	:	

Note: The first two boxes in the initials are filled in with the first two letters of the two words of the name, and the third box is filled in with the date of birth. If the date of birth contains two numbers, use only one of them.

Example: Name: [name], Date of Birth: Januari 8th → [L|C|8].

MEDICAL HISTORY

History	Yes	No	Unknown
Have you ever had anaemia within the last 5 years?			
Do you have a history of kidney disorder?			
Do you have a history of stomach ulcers or GERD?			
Do you have a history of liver disorder?			
Are you an active smoker < 5 years?			
Are there any family members who smoke?			
Are you undergoing any medical treatment? Please specify!			

Signature of officer after filling out form:

Initials:

Date:

SAMPEL

Research Number:	Respondent's initials: []
------------------	---

SCREENING 2 – ANTHROPOMETRY AND BLOOD PRESSURE

ANTHROPOMETRIC EXAMINATION (PRE)	
Body weight : kg	Body height : cm
BMI : kg/m ²	
Waist Circumference: cm	
BLOOD PRESSURE MEASUREMENT (PRE)	
Blood pressure:	

ANTHROPOMETRIC EXAMINATION (POST)	
Body weight : kg	Body height : cm
BMI : kg/m ²	
Waist Circumference: cm	
BLOOD PRESSURE MEASUREMENT (POST)	
Blood pressure:	

Signature of officer after filling out form: Initials: Date:

SAMPEL

Research Number:	Respondent's initials: []
------------------	----------------------------

SCREENING 3 – BLOOD AND BIOCHEMICAL TESTS

a. Initial Screening

Parameters	Test Date/Time	Result	Status
Hematology Profile	[] / [] / [] (DD/MM/YY) [] . [] WIB	RBC : $10^6/\mu\text{L}$ HB : g/dL HCT : % MCV : fL MCH : pg	 Eligible  Not Eligible
Lipid Profile	[] / [] / [] (DD/MM/YY) [] . [] WIB	TC : mmol/L HDL : mmol/L LDL : mmol/L Tg : mmol/L	 Eligible  Not Eligible
Fasting Blood Glucose	[] / [] / [] (DD/MM/YY) [] . [] WIB	mmol/L	 Eligible  Not Eligible
ALT	[] / [] / [] (DD/MM/YY) [] . [] WIB	$\mu\text{kat/L}$	 Eligible  Not Eligible

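### As written, the rule for women admits only those who are married and sexually active, gives no reason, and no supplied criterion, history question or laboratory row excludes pregnancy or breastfeeding

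*Combined protocol and SAP*

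**What the plan says.** Section 6 limits participants to ages 20 to 35 and adds a condition for women only: "excluding women who were either unmarried or sexually inactive". The Subject paragraph of section 1.1 carries the same parenthesis. Neither place explains it, and nor does the rest of the supplied text.

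The other inclusion criteria in section 6 concern smoking and a history of anaemia, liver or kidney disease. Section 1.1 adds good health and no cardiovascular disease. The three exclusion criteria concern required medication or vitamins, discomfort with the product, and abnormal baseline biochemistry.

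First selection is described in section 1.1 as "an initial screening process based on the information provided in the Google Forms by prospective research subjects". That questionnaire is not among the supplied documents. Once consent is signed, section 7.4 provides that "each subject will be furnished with a set of fourteen tea bags, each containing four grams of white tea".

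On risk, section 2.3 says of polyphenols and iron absorption that the effect "may consequently result in iron deficiency and the subsequent development of anaemia". It says of catechins that "in excessive doses, they have the potential to cause excessive pro-oxidant effects, triggering inflammatory reactions, necrosis and steatosis in the liver". Section 7.5 withdraws subjects with abnormal baseline haematology, liver or kidney results; on the first of these it states: "Haematological tests are performed to ensure that the subject is not anaemic".

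**The concern.** A restriction tied to marital status and sexual activity looks like an indirect way of dealing with possible pregnancy. As worded, it works in the opposite direction: among women, it selects the group in which pregnancy is possible. No supplied check then identifies a woman who is pregnant or breastfeeding.

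What is at stake is participant safety and whether the eligibility rule can be applied as intended. Because both sections use the same words, neither can be used to correct the other. The estimated effect of the tea is not in question here.

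**Working it through.** **Step 1: what the parenthesis does.** A woman is excluded if she is unmarried OR sexually inactive. She is therefore admitted only if NOT (unmarried OR inactive), which is married AND active.

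| Married | Sexually active | Result |
|---|---|---|
| yes | yes | admitted |
| yes | no | excluded |
| no | yes | excluded |
| no | no | excluded |

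Men are unaffected.

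**Step 2: whether anything supplied excludes pregnancy or breastfeeding.**

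- Section 6, 3 inclusion and 3 exclusion criteria: neither condition is named.
- Section 1.1, the added conditions of good health and no cardiovascular disease: neither is named.
- Appendix 1, Screening 1, 7 medical history questions: anaemia, kidney, ulcer or reflux, liver, own smoking, family smoking, and finally "Are you undergoing any medical treatment? Please specify". Neither is named.
- Appendix 1, Screening 3, 9 baseline rows: haematology, lipids, fasting glucose, ALT, AST, creatinine, eGFR, urea, antioxidant enzymes. There is no pregnancy test.

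**Step 3: what might catch a pregnant woman incidentally.**

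- Exclusion a removes her if she is required to take medication or vitamins.
- Exclusion c removes her if her baseline biochemistry is abnormal.
- The withdrawal rule in section 7.5 removes her if baseline haematology, liver or kidney results are abnormal.

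None of these identifies pregnancy or breastfeeding as such. Suppose a pregnant or breastfeeding woman meets the age, smoking and marital conditions, has normal baseline results and no listed history, and needs no medication or supplement. She meets every supplied criterion at entry.

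**Step 4: exposure.** From section 7.4, 14 bags × 4 g = 56 g of white tea over 14 days, or 4 g a day.

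**Step 5: the plan's own number.** Section 6 takes 15 subjects and allows 20% dropout: 15 / (1 − 0.20) = 18.75, rounded up to 19. This reproduces the stated 19, and nothing in this point alters it. The split of the 19 by sex is not given, so the number of women affected cannot be computed.

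**The case against.** The strongest reply is that the parenthesis is a translation reversed by accident. If the intention was to exclude women who are married or sexually active, only unmarried and inactive women would enter, and the rule would largely do what is missing here. That may be so, but the documents do not confirm it. If it is so, the rule states the opposite of its intent and needs correcting. Even then, breastfeeding and an earlier conception would remain unaddressed.

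Second, the absence is inferred from incomplete material. The Google Forms questionnaire and the pages removed before review may contain a pregnancy item. Appendix 1 is plainly not the whole eligibility instrument, since it has no question on marital status, sexual activity or cardiovascular disease. This limits the weight of the form, but less so that of the criteria lists. Sections 6 and 7.1 say that selection follows the stated criteria, and those do not name either condition. If the questionnaire does ask, the supplied text gives no rule for acting on the answer.

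Third, no harm specific to pregnancy is shown. This stands. Section 2.3 names no pregnancy or lactation risk, its liver warning concerns excessive doses, and sections 2.1 and 2.2 present 4 g as the safer of the two doses considered. Existing anaemia and liver disorder are screened for in every subject.

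A reader might also infer that normal blood results alone would let any pregnant woman in. The documents do not support that, because exclusion a also applies and vitamins are barred during washout and treatment.

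**Conclusion.** The point holds for the supplied text, with moderate confidence. The literal rule restricts women to those who are married and sexually active without a reason, and no supplied criterion, history question or laboratory row excludes pregnancy or breastfeeding. This is a defect in the rule itself, not just a missing detail, and it merits a change.

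Its size can be given only as planned exposure: 56 g of white tea over 14 days for each woman who enters. The conclusion assumes that the parenthesis is applied as written and that the unseen questionnaire adds no exclusion of its own.

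Three stronger conclusions might be drawn, and none is supported:

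- That pregnant women were enrolled. The documents give no count of women and no pregnancy status.
- That this tea at this dose is harmful in pregnancy. No such risk is stated.
- That the day 0 to day 15 comparison or the sample size is compromised. Nothing here shows either.

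Counting how many possible readings of the parenthesis would admit sexually active women is not a measure of size either, since the documents give no basis for weighting them.

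**What to change.** 1. Add to the exclusion criteria in sections 1.1 and 6: *d. Women who are known or suspected to be pregnant, or who are breastfeeding.*
2. Add one row to the Screening 1 medical history, using its existing Yes / No / Unknown columns: *Women only: are you pregnant, do you suspect you may be pregnant (for example, a missed period), or are you breastfeeding?* Yes or Unknown means not eligible. The row asks about suspicion because asking whether a woman could be pregnant might rule out many of those whom the literal parenthesis admits.
3. Correct the parenthesis in both sections to its intended meaning, or delete it if it has no other purpose. The sponsor must say which.

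Section 1.1 states: "The total number of subjects included in the study was 19, with an age range of 20-35 years". Enrolment may therefore be over. If it is, report which reading was applied and how many women entered under it.

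The cost is a protocol amendment with ethics committee approval under section 14, and an unknown number of volunteers made ineligible. No visit or laboratory test is added, and the planned 19 does not change. Self-report will still miss a pregnancy that the woman does not suspect.

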All data pertaining to the study will be stored on CRFs/individual screening sheets. The data will be recorded in both soft and hard file formats on a daily basis.

Evaluation Criteria

Anthropometric measurements, blood pressure, haematology, and biochemistry tests will be conducted before the intervention and one day after the last intervention (day 0 and day 15). Anthropometric measurements, blood pressure, and blood sampling will be conducted at the Faculty of Pharmacy, Padjadjaran University. The biochemical examinations will be carried out at the clinical laboratory of the Bandung City Health Office, while the complete haematology and antioxidant enzyme examinations will be carried out at the Biomedical Laboratory of the Faculty of Medicine, Padjadjaran University. The results of the examinations conducted before and after the white tea intervention will be analyzed to ascertain the effect of white tea consumption over a period of 14 days. The types of food and beverages consumed by the research subjects and their daily activities were recorded in the CRF for a period of 28 days (from the wash-out phase to the observational phase).

Statistical Analysis

The effect of white tea administration will be compared before and after treatment using a t-test analysis.

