7. RESEARCH PROCEDURE

7.1. Recruitment of Respondents and Initial Screening

The data collected from respondents will undergo a review and selection process, with this being based on predetermined inclusion and exclusion criteria. A proportion of respondents who meet the specified criteria will be directed to undergo a 7-day washout period. The purpose of this procedure is to prevent bias in the initial screening process. During this phase, subjects are instructed to avoid the consumption of vitamins, herbal drinks containing spices (turmeric, ginger and galangal), fruits with high flavonoid content (grapes, apples, oranges and their processed products), and products containing high levels of tannins (coffee, other types of tea, and chocolate).

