10. QUALITY CONTROL AND ASSURANCE

10.1. Procedures at the Research Site

Standard Operating Procedures will be established for all relevant clinical and laboratory activities to ensure the quality of the research. Subject compliance will be monitored throughout the study to ensure adherence to the established inclusion and exclusion criteria. Researchers are obliged to sign and date all examination results, thereby confirming that said results have been reviewed. Researchers may appoint assistants to assist with the execution of research and the supervision of research assistants. Nevertheless, the onus for the research remains with the researcher.

Prior to the initiation of the research process, ethical approval will be sought. Researchers must ensure that all personnel have been adequately briefed and trained on SA GCP, ICH-GCP, protocols and all procedures for research purposes.

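### Exclusion criterion (b), discomfort while taking the tea, can only be met after dosing and could remove intolerant subjects from the day-0 to day-15 safety comparison

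*Combined protocol and SAP*

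**What the plan says.** Exclusion criterion (b) has the same wording in Section 1.1 (Subject) and Section 6: "The subjects reported experiencing discomfort during the administration of the product". Its neighbour, criterion (c), is limited in time: "Prior to the initiation of treatment, biochemical results were found to be outside the normal range". Criterion (b) has no such limit.

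The criteria are meant for screening. Section 6 applies them to the recruitment-form data, and Section 7.1 says: "The data collected from respondents will undergo a review and selection process, with this being based on predetermined inclusion and exclusion criteria". The tea comes later. Under Section 7.4, once the consent form is signed, "each subject will be furnished with a set of fourteen tea bags". No run-in or test dose is described.

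Section 10.1 extends the criteria beyond screening: "Subject compliance will be monitored throughout the study to ensure adherence to the established inclusion and exclusion criteria".

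One of the two aims in Section 2.1 is "to ensure the safety of using this dose for 14 days". Section 2.3 lists a burning sensation among the known risks and says of caffeine that it "has been demonstrated to induce adverse effects, including symptoms such as nausea and vomiting". Under Evaluation Criteria, Section 1.1 says: "The results of the examinations conducted before and after the white tea intervention will be analyzed". Section 7.5 schedules blood on days 0 and 15, and Section 8 names a t-test or a Wilcoxon test. None of these three places says what happens to a subject excluded after dosing.

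**The concern.** A rule that depends on how a subject reacts to the product is a rule about outcome, not eligibility. It cannot work at the only point where the plan describes applying it. If staff follow it later, as Section 10.1 allows, it removes the subjects who did not tolerate the tea.

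Safety here is judged by haematology, liver and renal values before and after 14 days of tea, with no control group. Section 1.2 makes further development as an adjuvant depend partly on those values being acceptable. If intolerant subjects are left out of the comparison, it cannot show whether their laboratory changes differed from everyone else's, and there is no second arm in which the selection would show up.

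**Working it through.** **Can (b) operate before dosing?**

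- Section 1.1 uses the word administration for the 14-day tea stage.
- The product is first supplied after consent (Section 7.4), with no run-in.
- The medical-history form in Appendix 1 asks about stomach ulcers or GERD. It does not ask about earlier discomfort with tea.

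As worded, (b) can therefore only be met after the first cup.

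**What happens to a subject who meets it?** Section 7.6 provides health monitoring after a medical stop. It mentions neither a day-15 sample nor whether the data are kept. Both tests in Section 8, used before-after, need two values per subject. A subject without a day-15 value drops out, and no analysis set is named that would keep a subject who has one.

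**Sample size.** Section 6 starts from 15 subjects and allows 20% dropout: 15 / 0.8 = 18.75, rounded up to 19. This agrees with the plan. Up to 19 − 15 = 4 subjects can be lost with the target of 15 still met.

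**Possible effect on a mean change.** Let k be the number omitted and D the difference between their mean change and that of the rest, in SD of change. The documents give neither, so both are assumed. The all-dosed mean differs from the retained mean by k × D / 19. The standard error of the mean change with 19 subjects is 1/√19 = 0.229 SD.

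| k | Shift, D = 1 | Ratio to SE | Shift, D = 2 | Ratio to SE |
|---|---|---|---|---|
| 1 | 0.053 SD | 0.23 | 0.105 SD | 0.46 |
| 2 | 0.105 SD | 0.46 | 0.211 SD | 0.92 |
| 4 | 0.211 SD | 0.92 | 0.421 SD | 1.84 |

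Five of the six cases lie within one standard error.

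**Possible effect on individual abnormal values.** If no abnormal day-15 value is seen among the retained subjects, the share among all 19 dosed could still be as high as k/19: 1/19 = 5.3%, 2/19 = 10.5% or 4/19 = 21.1%. This is a worst case in which every omitted subject is abnormal.

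**Is it likely to arise?** At an assumed discomfort rate p, the chance of at least one case among 19 is 1 − (1 − p)^19. This gives 62% for p = 5%, 86% for p = 10% and 99% for p = 20%.

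**The case against.** The strongest reply is that the harm needs three steps the documents never state: (b) is applied after dosing, the subject then misses day 15 or is dropped, and that subject's laboratory change differs. Section 7.5 schedules day-15 blood without exception, Section 9.1 wants a completed CRF for every subject, and the sentence in Section 10.1 is general quality control. Section 2.3 also attributes the symptoms to theophylline and caffeine, but liver injury to excess catechins and anaemia to polyphenols, so discomfort need not go with laboratory change. The mean shifts above are mostly small.

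Tolerability information is also kept. Complaints are recorded daily on a 28-day checklist, subjects stopped for medical reasons are followed, all subjects have a seven-day observation phase, and the audit verifies side effects. Finally, the missing analysis set affects every dropout, not only those under (b).

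Most of this stands as a limit on size. It shows that the harm is conditional, that any bias in the means is probably modest, and that discomfort itself can still be reported. It does not make (b) workable at screening, supply day-15 values, or say who is analysed. Reading (b) as past intolerance of tea fits neither its wording nor the screening form, and would in any case require rewording. The wider gap in Section 8 does not excuse (b), which is a written instruction to select on an expected effect of the product.

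**Conclusion.** The concern holds in its conditional form. Criterion (b) is misplaced: it can only be met after dosing. If it is used to remove treated subjects, the day-0 versus day-15 safety comparison could leave out those who did not tolerate the tea. The documents do not show that this will happen, and they give neither a discomfort rate nor a link between discomfort and laboratory change. On the assumed inputs the mean change moves by 0.05 to 0.42 SD against a standard error of 0.23 SD, so the effect on means is probably small. The more relevant loss is of individual abnormal values, in up to 4 of 19 subjects if the whole dropout allowance were used this way. It should be fixed because safety is a stated aim and the correction is cheap. Confidence is medium, because the consequence depends on how the site would apply the rule.

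**What to change.** - Delete (b) from the exclusion criteria in Sections 1.1 and 6, and list discomfort in Section 7.6 as a reason to stop the tea.
- In Section 8, define the safety set as every subject who drinks at least one tea.
- Ask subjects who stop early to attend the day-15 measurements already planned. Include their values in the all-dosed comparison, and list them separately with doses taken and days since the last dose.
- Report discomfort and withdrawals, with reasons, out of all dosed subjects, using the daily complaint records.

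The cost is protocol wording and one listing; the sample size stays at 19 and no visit is added. The main drawback is partial exposure. Days since the last dose at day 15 equal 15 minus the day of that dose: 12 days for a stop after day 3, 8 days after day 7, and 1 day for completers. Early stoppers' values may therefore be diluted toward no change, which is why the separate listing is needed. Reported tolerability may also look slightly worse.
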